14.0 ANALYTICAL PLAN

14.1 Statistical Hypotheses

Primary Efficacy Endpoint: It is hypothesized that BUP/NX detoxification, compared to clonidine, will be associated with a better treatment response. A treatment responder is defined as anyone who completes the 13-day detoxification and whose last urine specimen is negative for opiates. By combining treatment retention with opiate abstinence, a composite number is derived that is indicative of both the patients' tolerance to the treatment and the desired outcome of abstinence at the completion of a short-term detoxification procedure. Note that there is no issue concerning the handling of missing data when utilizing this definition of "responder." Patients who fail to either come in or provide a urine sample are, by definition, non-responders.

Other Primary Efficacy Endpoint: Other primary efficacy endpoints were selected to examine the effect of treatment on 1) opiate and other drugs of abuse abstinence throughout the detoxification period and during longer term follow-up, 2) withdrawal symptoms, 3) treatment retention, 4) safety, 5) patient satisfaction with the treatment and 6) extent of ancillary medications dispensed to provide a comprehensive overview of the clinical efficacy and safety of the two treatment regimens.

Hypotheses for the other primary outcome measures include that BUP/NX detoxification, compared to clonidine, will:

- 1. Increase the number and consecutive duration of opiate and all drug-free urine specimens during detoxification and follow-up.
- 2. Increase the number of days retained in treatment.
- 3. Decrease the amount of ancillary medications needed to treat withdrawal symptoms.
- 4. Lessen the severity of withdrawal symptoms as assessed by COWS, ARSW, and VAS.
- 5. Lessen the severity of dependence or abuse as assessed by ASI Lite.

6. Improve the quality of life as assessed by the SF-36 questionnaire and satisfaction with treatment (CSQ).

14.2 Outcome Measures

14.2.1 Primary Outcome

One primary outcome measure is the number of treatment responders in each group out of all of the patients randomized to that group (intent-to-treat population).

14.2.2 Other Primary Outcomes

Other Primary outcomes include:

- 1. The number of urine specimens negative for opiates per patient (a maximum of 4 per patient).
- 2. The number of consecutive urine specimens negative for opiates per patient (maximum of 4).
- 3. The number of urine specimens negative for all drugs (opiates, methadone, cocaine, amphetamines, benzodiazepines, and cannabinoids) per patient (a maximum of 4 per patient).
- 4. The number of days retained in treatment (total days in treatment is the number of days since the start of treatment and the last day of treatment).
- 5. The frequency of dispensing of ancillary medications, by indication (anxiety or restlessness, bone pain or arthralgias, nausea, diarrhea, or insomnia).
- 6. The probability of remaining in treatment and being opiate-free at each urine collection.
- 7. The probability of remaining in treatment and being totally drug-free (negative urine tests for opiates, methadone, cocaine, amphetamines, benzodiazepines, and cannabinoids) at each drug collection.
- 8. The number and severity of adverse events.
- 9. The COWS score during treatment and 1-month follow-up.
- 10. The ARSW score during treatment and 1-month follow-up.
- 11. The VAS score during treatment.
- 12. The ASI Lite score during follow-up.
- 13. The CSQ score at the final visit.
- 14. The SF-36 score during follow-up.

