DURATION OF THE STUDY: The total duration of study participation for each patient will be a maximum of 6 months consisting of: screening and baseline assessments; detoxification (13 days); and, follow-up evaluations conducted at 1, 3, and 6 months after enrollment. It is estimated that 2 patients will be enrolled per site per week with a total of 6 sites. Thus, the estimated length of enrollment is 30 weeks.

SAFETY ASSESSMENTS: Before any study procedures are performed, patients will be required to provide signed informed consent. All candidates for study enrollment will have a physical examination including vital signs and weight, medical history and history of prior medication use assessment, and psychiatric evaluation (ASI Lite) including a DSM-IV checklist for substance dependence, HIV risk assessment, and clinical laboratory studies (blood chemistry, hematology, Hepatitis B and C serology, and urinalysis) performed during screening/ baseline. All patients will have a 12-lead electrocardiograph (ECG). Females will be given a pregnancy test. Assessments of adverse events (AEs) and concomitant medication use will be performed daily during detoxification and at the one-month visit. Serious Adverse Events (SAEs) will be reported during the treatment and follow-up phases of the study.

OUTCOME ASSESSMENTS: Abstinence from opiates, amphetamines, cocaine, cannabinoids, methadone, and benzodiazepines will be assessed by urine drug screen measured at baseline, throughout detoxification, and at follow-up. Treatment retention will be calculated as the number of days each patient received his/her detoxification medication. The patient's status in the study will be tracked with a Study discharge report (SDR). The dispensing of ancillary medications will be tallied and grouped according to symptomology (several medications are permitted for treating anxiety, insomnia, nausea, etc.) and day during detoxification. Withdrawal symptoms will be assessed using the clinical opiate withdrawal scale (COWS), the adjective rating scale for withdrawal (ARSW), and visual analog scales (VAS) during detoxification and at follow-up (COWS and ARSW only). Additional measures of overall treatment effect will include a

shortened version of the Addiction Severity Index (ASI Lite), a client satisfaction questionnaire (CSQ), and SF-36 Health-related Quality of Life questionnaire administered at baseline and all follow-ups.

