11.6 Ancillary Medications

All participants will have the option to receive ancillary medications. Dispensing of any medications will be recorded on a CRF. Dispensing of ancillary medications will be at the physician's discretion in accordance with clinical need to assist with the management of withdrawal signs and symptoms during detoxification but should be limited only to those medications listed below. Each type of ancillary medication will be placed into its own childproof bottle, appropriately labeled with the patient's name, date issued, contents and expiration date as well as dosing instructions for the patient. At the start of the detoxification, patients will be instructed on the use of each medication and told they can self-administer the medications in accordance with the instructions provided on the childproof bottle. Refills will be available to all participants during each scheduled clinic visit. Use of ancillary medications will be closely monitored for the duration of the study interventions. The following lists the dose, schedule, and indication for use of ancillary medications:

For anxiety and restlessness:

Days 1-7

lorazepam 1-2 mg q 6 hours prn; NTE 8 mg/24 hour **OR** oxazepam 15 - 30 mg po q6 hours prn; NTE 120 mg per 24 hours **OR** phenobarbital 15 - 30 mg. po q6 hours prn; NTE 120 mg per 24 hours **OR** hydroxyzine hydrochloride 50 mg, po q6 hours prn; NTE 200 mg per 24 hours

Day 8-13

lorazepam 1-2 mg q 6 hours prn; NTE 8 mg/24 hour **OR** oxazepam 15 - 30 mg. po q6 hours prn; NTE 60 mg per 24 hours **OR** phenobarbital 15 - 30 mg. po q6 hours prn; NTE 60 mg per 24 hours **OR** hydroxyzine hydrochloride 50 mg, po q6 hours prn; NTE 200 mg per 24 hours

For bone pain and arthralgias:

Days 1-13

Non-steroidal anti-inflammatory agent, such as ibuprofen (Advil, Motrin and others) 800 mg po q8 hours with food;

NTE 3200 mg in 24 hours **OR**

acetaminophen (Tylenol and others) 650 mg q 4 – 6 hours NTE 3900 mg in 24 hours **OR** methocarbamol (Robaxin and others) 500-1000 mg po q6 hours prn; NTE 2000 mg per 24 hours

For nausea:

Days 1-13

trimethobenzamide (Tigan) 250 mg po q8 hours prn; NTE 750 mg per 24 hours or 100/200 mg suppositories; NTE 400 mg per 24 hours

For diarrhea:

Days 1-13

loperamide (Immodium) 2 mg, 2 caps followed by 1 cap after each unformed stool: NTE 8 mg per 24 hours. **OR**

Donnatal 1-2 tablets po q 6-8 hours prn; NTE 8 tablets per day

For Insomnia:

Days 1-13

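### Outcomes 3 and 7 count any benzodiazepine-positive urine as not drug-free, although the protocol itself supplies lorazepam and oxazepam during the same days

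*Protocol*

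**What the plan says.** Protocol section 14.2.2 lists 14 other primary outcomes. Outcome 3 is "The number of urine specimens negative for all drugs (opiates, methadone, cocaine, amphetamines, benzodiazepines, and cannabinoids) per patient", with a maximum of four. Outcome 7 is the chance of staying in treatment and "being totally drug-free (negative urine tests for opiates, methadone, cocaine, amphetamines, benzodiazepines, and cannabinoids) at each drug collection". The synopsis (section 3.0) reads such a result as abstinence: "Abstinence from opiates, amphetamines, cocaine, cannabinoids, methadone, and benzodiazepines will be assessed by urine drug screen".

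Section 11.6 opens ancillary medication to all participants at the physician's discretion. For anxiety and restlessness it lists "lorazepam 1-2 mg q 6 hours prn; NTE 8 mg/24 hour" in both the days 1–7 and days 8–13 blocks. Oxazepam is also in both blocks; the days 1–7 entry is "oxazepam 15 - 30 mg po q6 hours prn; NTE 120 mg per 24 hours". Phenobarbital and hydroxyzine are alternatives for the same indication, the latter as "hydroxyzine hydrochloride 50 mg, po q6 hours prn; NTE 200 mg per 24 hours".

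Sections 11.8 and 12.18 place the in-treatment urines on days 3 or 4, 7 or 8, 10 or 11, and 13 or 14. Section 12.20 has the type of ancillary medication dispensed logged daily. Hypothesis 3 in section 14.1 is that BUP/NX will "Decrease the amount of ancillary medications needed to treat withdrawal symptoms".

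**The concern.** A participant who takes only the lorazepam or oxazepam that the study supplied, and tests positive for it, is recorded as not drug-free. Outcomes meant to show abstinence from drugs of abuse then mix two things: use of non-study drugs, and the physician's choice of ancillary medication. The trial is open-label and dispensing is discretionary, so nothing in the design makes that choice equal in the two arms.

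Two errors can follow. If benzodiazepine use is similar in both arms, a real difference in abstinence shrinks. If use differs, a difference appears where none exists. Either way, the result on these two outcomes cannot be read as a statement about abstinence.

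The six-class panel is written into the outcome definitions themselves, so an analysis plan that follows the protocol would inherit the problem.

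**Working it through.** **Text check**

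| Element | Where | Content |
|---|---|---|
| Drugs that must be negative | 14.2.2, outcomes 3 and 7 | six classes, including benzodiazepines |
| Study-supplied benzodiazepines | 11.6 | lorazepam and oxazepam, days 1–13, both arms |
| In-treatment urines | 11.8, 12.18 | days 3/4, 7/8, 10/11, 13/14 |
| Exemption for dispensed drugs | 11.6, 12.18, 12.20, 14.2.2, 14.4 | none |
| Link from dispensing log to outcomes | 12.20, 14.2.2 | none |

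The protocol gives no figure for outcomes 3 or 7 or for benzodiazepine use, so there is nothing to reproduce. The sizes below are illustrations. Only the arm sizes (240 and 120, section 14.6) and the two-sided alpha of 0.05 (section 14.4) come from the document.

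**One collection (outcome 7)**

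Assumed inputs:
- *m*: share truly retained and negative for non-study drugs, taken as 30% in both arms
- *b*: share given a study benzodiazepine, independent of *m*
- *d*: chance that such a participant's specimen tests positive, taken as 1 unless stated

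Observed drug-free rate: p = m × (1 − b × d).

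Rejection probability: Φ[(|pB − pC| − 1.96 × se0) / se1], where se0 = √[p̄(1 − p̄)(1/240 + 1/120)] and se1 = √[pB(1 − pB)/240 + pC(1 − pC)/120].

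Example, use of 30% v 60%:
- pB = 0.30 × 0.70 = 0.21 and pC = 0.30 × 0.40 = 0.12
- p̄ = (240 × 0.21 + 120 × 0.12)/360 = 0.18
- se0 = 0.0430 and se1 = 0.0396
- (0.09 − 0.0842)/0.0396 = 0.147, so Φ = 0.56

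| Use, BUP/NX v clonidine | Observed drug-free | False difference | Rejected |
|---|---|---|---|
| 30% v 30% | 21% v 21% | 0 | 5% (nominal) |
| 30% v 40% | 21% v 18% | +3 points | about 10% |
| 20% v 40% | 24% v 18% | +6 points | 25% |
| 40% v 60% | 18% v 12% | +6 points | 30% |
| 30% v 60% | 21% v 12% | +9 points | 56% |
| 50% v 80% | 15% v 6% | +9 points | 72% |
| 30% v 60%, d = 0.5 | 25.5% v 21% | +4.5 points | 15% |
| 40% v 30% | 18% v 21% | −3 points | about 11%, against BUP/NX |

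**Count of negatives (outcome 3)**

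The false difference in mean count is 4 × m × d × (bC − bB). With m = 0.3, d = 1 and use of 20% v 40%, it is 4 × 0.3 × 0.2 = 0.24 specimens. Simulating 2,000 trials per scenario (beta-binomial counts, t-test), this was rejected in 47%. Use of 30% v 40% gave 0.12 specimens and 16%. Use of 30% v 60% gave 0.36 and 86%. Use of 20% v 40% with d = 0.5 gave 0.12 and 15%.

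**Dilution when use is equal**

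Assume a true 30% v 20% and 40% use in each arm. The observed rates are 0.30 × 0.6 = 18% and 0.20 × 0.6 = 12%. The power formula above gives 53% before dilution and 30% after.

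The 30% and 20% are borrowed from section 14.6, which claims 90% power for the primary outcome. That the same formula gives 53% is a separate matter, and this point does not depend on it.

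**After the change**

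If dispensed benzodiazepines are not scored, the false difference is zero whatever rates are assumed, and rejection under equal abstinence returns to about 5%.

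**The case against.** A reader might infer that the misclassification falls more often on the clonidine arm, so that outcomes 3 and 7 would favour BUP/NX. The document does not establish this. Its only support is hypothesis 3, which covers all ancillary medication, gives no rates and says nothing specific about benzodiazepines. Two non-benzodiazepine alternatives exist for anxiety, and the medications for pain, nausea, diarrhea and insomnia include no benzodiazepine. Hypothesis 2 also expects shorter retention on clonidine. A participant who has left already fails outcome 7 and cannot be misclassified. The direction is therefore conditional and could reverse.

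A reader might also say that these outcomes double-count ancillary dispensing (outcome 5). The overlap is limited to benzodiazepines given for one of five indications.

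The other side can add that the outcome driving the sample size is opiate-only, that only two of 14 other primary outcomes are touched, and that section 14.4 names only the opiate version for retention with negative urines. All of that stands, and it limits the weight of the point. Urine procedures are also deferred to an Operations Manual that is not shown. It is cited for specimen analysis, so a scoring exemption there cannot be assumed, but the absence of a rule is established only for this document.

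None of this removes the conflict between the definition and the permitted medication.

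**Conclusion.** The point holds as a defect in the in-treatment definition of outcomes 3 and 7: the rule scores protocol-dispensed medication as drug use. It calls for correction but does not bear on the primary outcome or on outcomes 1, 2 and 6, which use opiates only. Benzodiazepines are scheduled as ancillary medication only to day 13, so follow-up urines do not share the problem.

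The size cannot be fixed from the document. With equal true abstinence of 30% at one collection, false rejection starts at about 5% under equal use and reaches 56% to 72% only with a 30-point excess in the clonidine arm and full detection. It would favour BUP/NX only if hypothesis 3 holds for benzodiazepines in particular. The dilution of a real effect needs no difference between arms. All these figures rest on assumed rates of use, assumed detection, and independence between benzodiazepine receipt and other drug use.

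**What to change.** - For the in-treatment urines only, define outcomes 3 and 7 as negative for opiates, methadone, cocaine, amphetamines and cannabinoids. Align the wording of hypothesis 1 in section 14.1.
- Report in-treatment benzodiazepine results separately by arm, beside the Ancillary Medication Log entries for lorazepam and oxazepam.
- Give the six-class composite as a sensitivity analysis.
- Keep the full six-class panel at the 1, 3 and 6 month visits, where it remains informative.

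A rule that excuses every positive after any earlier dispensing is not a good substitute. One day-1 dispensing would mask all four in-treatment urines, and unevenly if dispensing differs by arm.

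The cost is wording; the log is already collected and no clinical procedure changes. The downside is small: illicit benzodiazepine use during detoxification leaves the main composite, and the log shows dispensing rather than ingestion, so attribution of a positive stays imperfect. The separate report and the sensitivity analysis keep that information visible.

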14.3 Intent-to-Treat and Evaluable Patient Populations

The intent-to-treat population is defined as the patients who are randomized to treatment. The evaluable population is defined as the patients who are properly qualified to participate in the study in accordance with the inclusion and exclusion criteria and who complete the 13-day detoxification procedure.

14.4 Analysis Plan

Baseline characteristics of groups will be generated using demographic data from intake questionnaires as well as the Addiction Severity Index. Information summarized will include gender distribution, age, years of use, route of administration, ethnic distribution, education, income, and ASI composite scores. Appropriate 2-sided *t*-tests or chi-square tests will be used to test for equivalence between groups. Inequalities between groups at baseline will be used as cofactors in analyses of outcome variables if related to outcomes.

Each of the primary and other primary outcome measures will be analyzed for the intent-to-treat population. The primary outcome measure is based on an intent-to-treat principle, and therefore cannot be analyzed in the evaluable population. The other primary outcome measures, however, will be analyzed for the evaluable population in addition to the intent-to-treat population. By examining the other primary outcome measures for the evaluable population, the long-term efficacy in treatment responders can be explored. Comparing results from the intent-to-treat and evaluable population analyses will also provide estimates of the effect of missing data. Major differences in the results, if any, will be further explored. While there is every intent to be complete in describing the analyses to be performed, it is not possible to anticipate every contingency, and some adjustments may be required to meet constraints posed by the structure of the data.

The primary outcome measure, treatment responders, will be compared between groups using the Chi-square statistic. Two-group two-tailed t-tests and analysis of variance (with repeated measures where appropriate) will be used to evaluate group differences in other primary outcomes, including retention, number of negative urines and number of consecutive negative urines, and frequency of ancillary medications dispensed. Survival analysis techniques including log- rank statistics will be used to evaluate treatment response over the duration of treatment and follow-up. Both retention in treatment and retention in treatment with negative urine tests for opiates will be evaluated. Repeated measures such as the ASI, VAS, COWS, ARSW will be evaluated using an appropriate repeated measures test such as generalized estimating equations.

Statistical tests will be two-sided, with alpha set at 0.05. Confidence intervals will be two-sided with a 95% confidence coefficient.

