11.5.2 Clonidine

Patients receiving oral clonidine will be instructed to swallow all pills and/or to leave their clonidine patch in place until replaced by medical personnel or until medical personnel directs the patient to change their dosage. The clonidine detoxification protocol was designed to reflect what is being used in clinical practice at a number of the participating CTP sites. Patients will be seen daily, on days of outpatient clinic operations.

In outpatient CTP sites, clonidine detoxification should be started early in the week (Tuesday or Wednesday [see section 11.4]) to insure a steady state level before the weekend with less medical staff. Medical personnel familiar with clonidine need to be available during clonidine treatment for daily patient monitoring, dose adjustment, and prescribing ancillary medication. Medical personnel should be familiar with monitoring vital signs for orthostatic changes and responding to any changes noted. Insure consistency in monitoring by using the same B.P. device at each visit.

Clonidine Dosing Procedure:

Day 1:

Encourage patients to drink lots of fluid. Dehydration exaggerates the hypotensive effects of clonidine. Before administering the test dose of clonidine, ask patients for any history of hypertension or hypotension, fainting or dizziness on rising. Take vital signs noting especially the systolic B.P. Check the EKG to insure the PR interval is not prolonged i.e. > .20 seconds. If the patient has systolic B.P. < 100 mm Hg or heart rate < 56 bpm, do not proceed with the clonidine test dose. Reassess patient if clinically warranted or discontinue the patient from the study.

Be cautious with patients with a history of hypertension or hypotension, fainting or dizziness on rising. Instruct all patients to get up slowly while taking clonidine (e.g. "sit up, swing your feet, and count to 10 before getting up").

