An AE is defined as any reaction, side effect, or untoward event that occurs during the course of the clinical trial, whether or not the event is considered medication-related or clinically significant. For this study, AEs will include events reported by the patient. A new illness, symptom, sign or worsening of a pre-existing condition or abnormality is considered an AE. Stable chronic conditions, such as arthritis, which are present prior to clinical trial entry and do not worsen are not considered AEs. All AEs must be recorded on the AE Form. The AE Form is also used to record follow-up information for unresolved events reported on previous visits.

Each week, a study investigator must review the AE Form completed for the previous week for any events that were reported as continuing. All AEs regardless of severity, will be followed by study investigators until satisfactory resolution. AEs may be reported up to 4 weeks following completion of detoxification.

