APPENDIX IV: Instructions For Evaluating and Reporting Adverse Events

A. GENERAL INSTRUCTIONS

- 1. The Adverse Events (AE) form must be completed at each study visit.
- 2. If no AEs occur, check the box marked NONE and sign and date form.
- 3. Enter only AEs that occur after the patient begins taking the investigational agent.
- 4. Enter only **one** AE per line.
- 5. Record the patient's description of the event, including all signs/symptoms reported.
- 6. Report the severity of the event according to the grading scale below.
- 7. Report the relatedness of the event to the study medication administration (see section C. below for guidance in determining relatedness).

B. DEFINITIONS – SEVERITY OF EVENTS

1 = Mild: Awareness of symptom, but easily tolerated.

2 = Moderate: Discomfort enough to cause interference with usual activity.

3 = Severe: Incapacitating with inability to work or do usual activity.

4 = Life threatening: At immediate risk of death.

C. DEFINITIONS – RELATEDNESS OF EVENTS

Study physician must review the information and offer an educated opinion about the relatedness of the event to the study drug. Do not use 'UNKNOWN' unless there is absolutely no information available upon which to base an opinion. Do not leave blank.

Use codes provided:

1 =**Definitely** – The adverse event:

- a) Follows a reasonable temporal sequence from drug administration.
- b) Abates upon discontinuation of the drug (de-challenge).
- c) Is confirmed by reappearance of the reaction of repeat exposure (rechallenge).

2 =**Probably** – The adverse event:

a) Follows a reasonable temporal sequence from drug administration.

- b) Abates upon discontinuation of the drug (de-challenge).
- c) Cannot be reasonably explained by the known characteristics of the patient's clinical state.
- 3 =**Possibly** The adverse event:
 - a) Follows a reasonable temporal sequence from drug administration.
 - b) Could have produced by the patient's clinical state or by other modes of therapy administered to the patient.
- 4 = **Remotely** The temporal association between the adverse event and the drug is such that the drug is not likely to have had any reasonable association with the observed event. Temporal association is defined as an association between a drug and the observed reaction or event such that the drug was present prior to the reaction or event as defined by history or drug blood level.

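### Adverse events are analysed on all randomised patients but entered only after the first dose, so each arm's rate is diluted by its undosed patients, and no treated set is defined

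*Protocol*

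**What the plan says.** Section 14.2.2 lists "The number and severity of adverse events" as item 8 of the other primary outcomes. Section 14.4 then says "Each of the primary and other primary outcome measures will be analyzed for the intent-to-treat population" and makes no exception for safety. It also sends all the other primary outcomes to the evaluable population.

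Section 14.3 defines both sets. For the first: "The intent-to-treat population is defined as the patients who are randomized to treatment". No dose is required. The second consists of properly qualified patients "who complete the 13-day detoxification procedure". There is no set of treated patients.

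On recording, Appendix IV, item A.3, reads "Enter only AEs that occur after the patient begins taking the investigational agent". Section 13.6 is wider: an adverse event is "any reaction, side effect, or untoward event that occurs during the course of the clinical trial", with no first-dose condition.

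Two further passages bear on who may go undosed. In 11.5.2, if day-1 systolic pressure is below 100 mm Hg or heart rate is below 56 bpm, the instruction is "do not proceed with the clonidine test dose. Reassess patient if clinically warranted or discontinue the patient from the study". Section 11.5.1 has no corresponding blood-pressure or pulse check for BUP/NX. But inclusion criterion 2 in 9.1 applies the same two limits to every patient before randomisation.

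**The concern.** An analysis on all randomised patients suits the responder outcome, where 14.1 counts absence as failure by definition. It does not suit adverse events that are collected only from the first dose. There, a patient who was never exposed enters the calculation as a patient without harm. The completer set errs in another way: it removes patients who left early, including those who left because they did not tolerate the drug. The protocol therefore assigns adverse events to two sets, and neither describes harm among patients who took the drug.

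Safety is one of the stated objectives in section 5.0, and it is compared between arms. If the arms differ in how many randomised patients are never dosed, a difference in adverse-event rates can appear, shrink or reverse for reasons unrelated to either drug.

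**Working it through.** **Inputs from the protocol.** Arms of 240 (BUP/NX) and 120 (clonidine), from 14.6; all-randomised denominator, from 14.3 and 14.4; event entry from first dose, from Appendix IV. The protocol gives no adverse-event rate and no expected number of undosed patients, so it has no figure of its own to reproduce here. The rates and undosed fractions below are assumptions.

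**Formula.** Let N be the number randomised to an arm, u the fraction never dosed, and p the proportion of dosed patients with an event. Events come only from the N(1 - u) dosed patients, so

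reported rate = p × N(1 - u) / N = (1 - u) × p.

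The same factor applies to the mean number of events per patient. For the comparison,

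reported ratio (clonidine / BUP/NX) = [(1 - u_clon) / (1 - u_bup)] × ratio among dosed patients.

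**Small fractions.** With p = 40%: at u = 1% the rate is 0.99 × 40 = 39.6%, a loss of 0.4 points; at u = 2% it is 0.98 × 40 = 39.2%, a loss of 0.8 points.

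**No true difference, p = 40% in both arms.**

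| Undosed, clonidine | Undosed, BUP/NX | Reported, clonidine | Reported, BUP/NX | Ratio |
|---|---|---|---|---|
| 5% | 5% | 38.0% | 38.0% | 1.00 |
| 5% | 0% | 38.0% | 40.0% | 0.95 |
| 10% | 2% | 36.0% | 39.2% | 0.92 |
| 20% | 2% | 32.0% | 39.2% | 0.82 |
| 2% | 10% | 39.2% | 36.0% | 1.09 |

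In the third row, 10% of 120 is 12 undosed clonidine patients. Equal fractions leave the ratio unchanged, although both rates are too low. The last row shows the bias reversing.

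**A true excess on clonidine, 40% against 30% among dosed patients (10 points).** With 10% and 0% undosed, the plan shows 36.0% against 30.0%, or 6 points. With 20% and 2%, it shows 32.0% against 29.4%, or 2.6 points.

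**If 13.6 governs instead of Appendix IV.** Let q be the event rate recorded among undosed patients. The reported rate becomes (1 - u)p + uq, which falls short of p by u(p - q). The shortfall vanishes only if q equals p, and the result then mixes exposed and unexposed patients.

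**The case against.** A reader might go further and infer that the plan by design hides clonidine's harms, because only clonidine has a pre-dose stop and an open-label assignment lets disappointed patients leave. The protocol does not support that.

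- The day-1 limits match entry criterion 2, which both arms must meet, and 11.4 requires a physician or investigator to verify eligibility before randomisation. The stop reaches only patients whose readings fall afterwards, and it allows reassessment as well as discontinuation.
- The clonidine-only PR-interval check is likewise narrowed by the exclusion of clinically significant ECG abnormalities in 9.2.
- Detoxification begins in an inpatient setting (7.0, 8.0), which limits loss between randomisation and first dose.
- Section 11.4 says the 2:1 ratio should help recruitment, which suggests that BUP/NX was expected to be the preferred arm. That makes departure after a clonidine assignment credible, but nothing indicates how often it would happen.

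Three other objections deserve weight. First, a safety set is commonly left to the SAP. That would answer a silent protocol, but this one assigns every outcome to a population and includes adverse events; its allowance for adjustments concerns the structure of the data and creates no safety set. Second, the adverse-event tables in 14.5 name no denominator, and the dosage log in 12.19 would let anyone recover the undosed count. This makes the defect easy to repair; it does not remove the stated rule. Third, it is too strong to say that an undosed patient can never contribute an event: 13.6 has no first-dose condition, and 13.7 requires serious events to be reported throughout the investigation. This stands, and it exposes an inconsistency that itself needs resolving.

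**Conclusion.** The point holds as a defect in the stated analysis population. Under 14.3, 14.4 and Appendix IV taken together, an arm's adverse-event rate is understated by its undosed fraction: relative to the rate among dosed patients, 5% undosed means 5% too low. That follows by arithmetic and assumes only that sites follow the form instruction.

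The effect on the comparison depends on the difference between the undosed fractions, which the protocol does not give. A bias against detecting clonidine harms is plausible from the pre-dose check in 11.5.2 and the open-label design. It is not established, and the opposite bias or none is also compatible with the documents. If only 1 to 2% go undosed, an assumed 40% rate moves by less than 1 point and the matter is minor; it becomes material only if undosed patients are numerous and uneven between arms. The evaluable analysis offers no protection, because it selects patients who tolerated the full 13 days. This is a worthwhile correction chiefly because it costs so little.

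**What to change.** - In 14.3, define a safety set: all randomised patients who received at least one dose of BUP/NX or clonidine.
- In 14.4, assign outcome 8 to that set in place of the intent-to-treat and evaluable populations.
- Report, by arm, the number randomised but never dosed beside the adverse-event results, so that a reader can see whether the arms differ.
- Reconcile the adverse-event definition in 13.6 with Appendix IV, item A.3, so that sites and analysts work from one rule on when an event counts.

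The cost is a few sentences and one more analysis set. No new data are needed, since daily doses are already logged under 12.19. The drawback is that the adverse-event comparison no longer rests on everyone randomised, so a difference between arms in who gets dosed could affect it; the never-dosed counts make that visible.
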